**Confidential**

Protocol #: COVMOPO0561

Rev E 09AUG2017

lower acuity unit, the subject should be withdrawn from the study. If subject meets eligibility criteria daily, subject will resume SM procedures and daily tracking of eligibility criteria

### **Surveillance Monitoring (SM) Group**

Subjects in the SM group will alternatively be admitted to a medical surgical unit and placed with the study device following study enrollment. Hospital staff will utilize SM for the duration of study enrollment.

The sponsor and investigator will collaborate to implement the SM strategy. This implementation could include a variety of strategies based on the site's facilities, staffing resources, and IT infrastructure. The Vital Sync™ IM & VPMP conveys physiologic data, waveforms, and will provide visual alerts and annunciation alarms. Alert and alarm thresholds will be customized as needed to align with the hospital's protocols. Data from the remote monitoring platform will be accessed at a central workstation, a workstation on wheels, a bedside tablet, and/or smartphones/tablets.

Subjects will be tracked daily to confirm continuing eligibility for the study. Temporary alternate monitoring modalities will be allowed per the discretion of the Investigator. If subject no longer meets eligibility criteria, the subject should be withdrawn and study completion date will be the date the subject became ineligible not the date the study team discovered the ineligibility.

If a subject is transferred to another hospital unit, subject will continue to be enrolled in the study. However, the subject will be removed from SM during the transfer including placement of BioModule. When the subject transfers back to the medical-surgical unit, SM should resume as soon as reasonably possible per discretion of the Investigator until discharge from the hospital or end of study enrollment.

If subject is transferred to ICU, there will be an exception to the requirement of tracking daily continuing eligibility. It is expected for additional care and monitoring to be administered during the ICU stay and AHA indication to change. Once subject is transferred from the ICU back to a lower acuity unit, eligibility criteria will be reassessed and documented. If subject no longer meets eligibility criteria upon return to lower acuity unit, the subject should be withdrawn from the study. If subject meets eligibility criteria daily, subject will resume SM procedures and daily tracking of eligibility criteria.

[figure not shown]
This document is electronically controlled. Printed copies are considered uncontrolled.

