### 6.2.3. Definition of Clinical and Qualitative Endpoints

1. RRT interventions

**Definition:** RRT's that are activated due to clinical deterioration as reported by the hospital or subject's medical record.

2. Survival rates post RRT interventions

**Definition:** Survival at discharge or study completion following RRT activation.

3. Code blue rates

**Definition:** Code blue teams that are initiated due to cardiopulmonary arrest as reported by the hospital or subject's medical record.

4. Unplanned intubations

**Definition:** An intubation and mechanical ventilation that was not planned during the course of the hospital stay.

5. Time of RRT activation to time of a threshold notification(s) from the SM system following clinical deterioration events

**Definition:** Time of RRT activation is the time that a clinician called or initiated the RRT team. Time of a threshold notification(s) is the time when the SM system alerts or alarms when a hospital protocol-defined threshold is exceeded.

6. Clinical team satisfaction with surveillance monitoring and study product

**Definition:** Clinical team (nurse or physician) who treated at least one study subject will be asked to take a qualitative survey on satisfaction and confidence.

7. Patient satisfaction with surveillance monitoring and study product

**Definition:** Each subject will be asked to take a qualitative survey on satisfaction and comfort and the end of enrollment.

8. Perceptions of clinicians who prescribe telemetry to patients without AHA indication

**Definition:** Each eligible clinician will be asked to take a qualitative survey focused on the AHA guidelines and the monitoring modalities of the study.

9. Clinicians' perceptions on telemetry utilization and impact on hospital resource utilization and patient flow

This document is electronically controlled. Printed copies are considered uncontrolled.

**Definition:** Each eligible clinician will be asked to take a qualitative survey focused on telemetry utilization and the monitoring modalities of the study.

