## 10.10. Subject Withdrawal or Discontinuation

During the course of this study, subjects may elect to be or may be withdrawn from further treatment for any of the following reasons:

- The subject may withdraw from the study for any reason without prejudice
- The clinician or investigator may terminate the study at their discretion
- Subject is prescribed additional continuous monitoring after enrollment
- Within the first 12 hours of study participation, subject is discharged from hospital or removed from the study for any reason
- Subject no longer meet study inclusion/exclusion criteria
- Technical issues that prevent continuous data collection from the Vital Sync™ IM & VPMP
- Sponsor terminates the study
- Other

Subjects may withdraw from the study at any time and for any reason. If a subject officially withdraws from the study, the investigator will document the reason and collect final outcomes data from the subject's medical record. No additional follow-up will occur for withdrawn subjects.

Subjects may only be replaced if they are a screen failure OR are withdrawn from the study during the first 12 hours of enrollment for any reason.

Withdrawal or discontinuation from the study will not affect the subject's regular care/hospitalization in any way.

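### Withdrawal on lost eligibility ends SAE recording and can fix post-RRT survival before discharge, and the plan does not say whether withdrawn subjects stay in the primary LOS analysis

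*Protocol*

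**What the plan says.** Protocol 10.1 has eligibility tracked daily in both groups. On loss of eligibility, "the subject should be withdrawn and study completion date will be the date the subject became ineligible"; the text for the telemetry (TM) group is the same. Tracking is suspended during an ICU stay, for this reason: "It is expected for additional care and monitoring to be administered during the ICU stay and AHA indication to change". Eligibility is reassessed afterwards: "If subject no longer meets eligibility criteria upon return to lower acuity unit, the subject should be withdrawn from the study". The ICU paragraph does not repeat the dating rule. Subjects who are still eligible resume study procedures.

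Protocol 10.10 lists further grounds on which a subject may be withdrawn, among them "Subject is prescribed additional continuous monitoring after enrollment" and "Technical issues that prevent continuous data collection from the Vital Sync" (the study platform, so surveillance (SM) group only). On withdrawal the investigator is to "collect final outcomes data from the subject's medical record", and then "No additional follow-up will occur for withdrawn subjects". SAP 7.4 repeats both statements and adds no analysis rule.

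Three other provisions take effect at withdrawal:

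- Protocol 12 and SAP 7.10 end adverse-event recording at discharge, at 30 (±2) days, or at withdrawal for any reason.
- Protocol 6.2.3 and SAP 4.2.3 define the post-RRT outcome as "Survival at discharge or study completion following RRT activation".
- Protocol 13.3 and SAP 7.1.3 base the primary analysis on evaluable data, a term that neither document defines. Protocol 13.1 counts withdrawals in its allowance for attrition.

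The primary endpoint, LOS, runs from admission to discharge (Protocol 6.2.1, SAP 4.2.1).

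**The concern.** Loss of eligibility here is plausibly tied to prognosis. A new AHA Class I or II indication, or a prescription for other continuous monitoring, is an exclusion criterion in Protocol 9.4 and is something that can follow a change in the patient's condition. The rule may therefore stop safety recording in the subjects most likely to have further events. SAP 7.2 compares adverse events between the groups with 95% confidence intervals, and Protocol 16.1 provides no data monitoring committee, so the recorded events are the main safety evidence.

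For the primary endpoint the question is narrower. The comparison is unblinded and not randomised (Protocol 10.5, 10.6). If the plan does not say whether withdrawn subjects count as evaluable, that choice can be made after LOS has been seen.

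**Working it through.** **Safety window and survival, from the text.** Take a subject with an RRT call who is managed without an ICU stay and then acquires an exclusion criterion while still in hospital.

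1. Protocol 10.1: withdraw, with completion dated to the loss of eligibility.
2. Protocol 12 and SAP 7.10: recording ends at withdrawal. A later SAE in the same admission is outside the window. An SAE between the loss of eligibility and its discovery falls after the back-dated completion date.
3. Protocol 6.2.3: survival at discharge and survival at study completion are now different readings, and no rule selects one.

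A subject who goes to the ICU stays enrolled there, so events in the ICU are captured. The same sequence starts only if the subject is ineligible on return.

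**Post-RRT mortality, illustration.** Recorded mortality = m(1 − w), where m is true in-hospital mortality after an RRT call and w is the share of those deaths that follow withdrawal. Both are assumed.

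- m = 10%, w = 10% to 50%: 9% down to 5%.
- m = 20%, w = 10% to 50%: 18% down to 10%.

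This shows under-recording, not a difference between groups.

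**The plan's sample size.** Inputs from Protocol 13.1: CV 0.65, ratio margin 1.2, 132 per group. SD of log LOS = √ln(1 + 0.65²) = 0.594; margin ln 1.2 = 0.182; SE = 0.594 × √(2/132) = 0.0731. Power at a true ratio of 1 and one-sided 0.05 = Φ(0.182/0.0731 − 1.645) = 80.2%. The stated 132 is reproduced.

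**Attrition.** 220 × 0.30 = 66 per group, leaving 154. Screen failures are included, so this gives no withdrawal rate. The SAP's 140 per group allows 1 − 132/140 = 5.7%.

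**LOS if withdrawn subjects are dropped, illustration.** Assume that the true SM/TM ratio among all who started monitoring is 1.20, that 132 per group are analysed, that withdrawn subjects stay k times as long as retained ones, and that the SM withdrawal proportion exceeds that in TM by d. Dropping them shifts the log ratio by −d·ln k. The chance of declaring non-inferiority is 1 − Φ(1.645 − d·ln k/0.0731).

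| d | k | ratio among retained | chance |
|---|---|---|---|
| 0 | any | 1.200 | 5.0% |
| 5 points | 1.5 | 1.176 | 8.6% |
| 10 points | 1.25 | 1.174 | 9.0% |
| 10 points | 1.5 | 1.152 | 13.8% |
| 10 points | 2 | 1.120 | 24.3% |
| −10 points (TM higher) | 1.5 | 1.2 × e^(0.0405) = 1.250 | 1 − Φ(2.200) = 1.4% |

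A simulation lets withdrawal occur at a daily hazard before discharge (lognormal stays, assumed mean TM stay 3 to 5 days, 132 per group starting, 20,000 runs per setting). With everyone kept to discharge the chance is 4.8–5.3%. With withdrawn subjects dropped it is:

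- equal hazards of 2% per day: 5.5–5.9%;
- equal hazards of 5% per day: 6.4–7.1%;
- SM 7%, TM 5%: 10.5–13.9%;
- SM 5%, TM 10%: 1.1–1.9%.

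Equal hazards still shift the result slightly, because the longer SM stays give more time to be withdrawn. When withdrawal is unrelated to stay, the chance remains 4.7–5.1%.

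**The case against.** **LOS.** LOS is defined to discharge, final outcomes data are required for withdrawn subjects, and Protocol 10.2.3 draws on medical and billing records. A subject with known admission and discharge times is ordinarily evaluable, and nothing in either document excludes the withdrawn. This stands. A reader might infer that LOS is cut at the back-dated date, or that withdrawn subjects are excluded. The documents support neither. The attrition allowance hints at exclusion but does not settle it.

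**Other events.** A reader might infer that later RRT calls, code blues, intubations and transfers are lost. Protocol 6.2.2 and 6.2.3 define these by hospital stay or by hospital or medical record, so that does not follow.

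**Frequency.** It is tempting to say that withdrawal is likely after an RRT call. The documents do not say so. The expected change in AHA indication is given as the reason for suspending tracking in the ICU. It is not said to persist on return, and RRT calls are not linked to ICU transfer. Protocol 10.1 also allows temporary alternate monitoring and keeps subjects enrolled through changes of unit, so added monitoring need not lead to withdrawal.

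**Error rates.** The eligibility rule is worded alike in both groups, the SM-only technical ground is not shown to relate to stay, and the larger figures need differential withdrawal that no passage supplies. This stands.

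**What the objection does not remove.** The requirement for final outcomes data lists no contents and does not override the explicit end of adverse-event recording. For survival it makes a discharge reading possible, but the definition still permits the earlier one.

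**Conclusion.** The safety gap holds on the text alone: with the plan followed exactly, SAEs after withdrawal in the same admission are outside the recording window. The survival endpoint is ambiguous, and one permitted reading fixes it before discharge. Both affect subjects found ineligible on return from the ICU or withdrawn without an ICU stay. How many that is cannot be derived from the documents, and the mortality figures only illustrate assumed inputs.

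For the primary endpoint the defect is a missing rule. Dropping withdrawn subjects would bias the LOS ratio only if withdrawal is related to stay and its pattern differs between groups: towards false non-inferiority if SM loses more long stays, against SM if TM does. The error rates above are conditional and should not be used to grade the point. It should be fixed because the safety window and the analysis set are easily made explicit. Confidence is moderate, since the frequency is unknown.

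**What to change.** Amend Protocol 10.10 and 12 and SAP 7.1.3, 7.4 and 7.10 as follows:

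- **Collection.** Withdrawal for any reason other than withdrawn consent ends study monitoring procedures but not outcome collection from records. SAEs and vital status are taken to discharge or the 30-day limit from the records already used at end of study (Protocol 10.2.3), by the same rule in both groups.
- **Survival.** Read post-RRT survival at discharge or the 30-day limit, never at a back-dated completion date (Protocol 6.2.3, SAP 4.2.3).
- **Primary set.** Define evaluable so that withdrawn subjects stay in with their actual discharge time. Protocol 10.10 allows replacement of subjects withdrawn in the first 12 hours, so state one rule for them in both groups and add a sensitivity analysis that includes them.
- **Sensitivity and reporting.** Present an analysis excluding withdrawn subjects as sensitivity only, with withdrawal counts and reasons by group.
- **Start of the 30 days.** Protocol 7.1 and 9.2 count from enrolment and Protocol 10.2.3 from hospital admission; reconcile them.

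The cost is a protocol amendment with its review, some added record review, and outcomes that include time off the assigned monitoring.

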**Confidential**

Protocol #: COVMOPO0561

Rev E 09AUG2017

Figure 1. Study Flowchart.

This document is electronically controlled. Printed copies are considered uncontrolled.

**Confidential**

## 10.2. Data Collection and Schedule of Events

The Schedule of Events (Table 1) summarizes the intervals and data collection procedures. Table 1 outlines the events that occur during both study phases and events that occur during only the TM and SM phase.

Applicable clinical data will be collected from the eMR or source documentation and entered into the eCRF. Clinical data will be entered electronically through two different secure systems:

- (EDC, Oracle Clinical): Enrollment, Baseline Assessments, Monitoring Group Assignment, Hospital History, Patient and HCP satisfaction, Adverse Events, Protocol Deviations, Device Deficiencies, will be collected through eCRF.
- Vital Sync™ IM & VPMP : Raw vital sign data from the SM system may be utilized to determine the time that the SM system detected a protocol defined activation threshold and thus activated an alarm notification. This will occur post-completion of each subject's enrollment and will occur only in subjects who had a RRT intervention and/or code blue. Alternately, alarm notifications generated by the Vital Sync™ IM & VPMP system may be utilized to determine changes in patient data relative to protocol defined thresholds and associated timing for those changes. Raw de-identified vital sign data will be collected throughout the duration of the study. All data may be used for future product development.

Healthcare economic and resource utilization data will be collected separately via hospital and billing records.

**Table 1. Schedule of Events**

Event/Activity to Occur Across All Phases			
Event/Activity	Screening/ Enrollment	Inpatient Days	End of Study
Informed Consent	X		
Inclusion/Exclusion Criteria 
 
Pregnancy test, if applicable
 
	X	X	
Baseline Assessments 
 
Demographics
 
Medical history
 
Primary diagnosis
 
Hospital admission data
 
Pregnancy test, if applicable
 
	X		
Monitoring Group Assignment	X		
Inpatient Tracking Form (daily eligibility)		X	
Hospital History data			X
Healthcare Economic data			X
Resource Utilization data			X
Adverse Events		X	X
Protocol Deviations		X	X
Device Deficiencies		X	X
eCRF Data Entry	X	X	X
Event/Activity to Occur During TM Phase Only			
Event/Activity	Screening/ Enrollment	Inpatient Days	End of Study
Telemetry Utilization Questionnaire for Clinicians (PRE)	X		
Perception Questionnaire for Prescribing Clinicians (PRE)	X		
Event/Activity to Occur During SM Phase Only			
Event/Activity	Screening/ Enrollment	Inpatient Days	End of Study
BioModule Placement	X		
BioModule Replacement (~every 24 hrs)		X	
Patient Satisfaction Questionnaire			X
Clinical Team Satisfaction Questionnaire			X
Telemetry Utilization Questionnaire for Clinicians (POST)			X
Perception Questionnaire for Prescribing Clinicians (POST)			X

This document is electronically controlled. Printed copies are considered uncontrolled.

### 10.2.1. Screening/Enrollment Visit

The first visit is the screening and enrollment visit. Patients considered potential candidates for the study based on pre-screening will sign informed consent form prior to participating in any study activities.

The following procedures and assessments will be performed **during both phases of the study** on the day of study enrollment and the results will be recorded on the subject eCRFs.

- Signed and dated informed consent
- Pregnancy test if applicable
- Verify that the subject meets all inclusion/exclusion criteria and collect the following:
  - Demographics
  - Medical history
  - Hospital admission data
- Assignment to monitoring group
- Assignment of study number
  - SM group will be a consecutive number beginning with 1001
  - TM group will be a consecutive number beginning with 2001
- Verify data and enter into eCRF within 5 preferred business days of collection

**During the TM Phase only**, the following procedures and assessments will be performed.

- Eligible clinicians complete Telemetry Utilization Questionnaire for Clinicians (PRE)
- Eligible clinicians complete Perception Questionnaire for Prescribing Clinicians (PRE)

**During the SM Phase only**, the following procedures and assessments will be performed.

- Attach BioModule to subject according to user manual instructions and keep device attached to subject for the duration of the evaluation or until fully charged BioModule is needed
- Link subject to BioModule using the Vital Sync™ VPMP
- Confirm that BioModule is communicating to Vital Sync™ VPMP by observing flashing green light on BioModule AND that HR, RR, and activity parameters are displayed on the central station

### 10.2.2. Inpatient Data Collection

Data collected during the course of the hospital stay will be limited to daily reviews of the subject status to assess continuing eligibility and to assess for AEs/SAEs, protocol deviations, and device deficiencies as applicable per Section 12.

The following procedures and assessments will be performed **during both phases of the study** on inpatient days and the results will be recorded on the subject eCRFs.

- Complete inpatient tracking form to confirm continuing eligibility for the study
- Check and record daily AEs/SAEs and protocol deviations
- Verify data and enter into eCRF within 5 preferred business days of collection

This document is electronically controlled. Printed copies are considered uncontrolled.

**During the SM Phase only**, the following procedures and assessments will be performed.

- Change-out BioModule as battery limits are reached, return the BioModule to the charging station
- Apply a new fully charged BioModule to the subject and link subject to new BioModule using the Vital Sync™ VPMP
- Clean reusable BioModule and return to the charging station
- Perform daily checks to confirm BioModule and the Vital Sync™ VPMP are communicating and operating properly
- Assess for and document any device deficiencies

### 10.2.3. End of Study Visit

The last visit will be on the day the subject is discharged from the hospital or at day 30 ( $\pm$  2 days) of hospital admission. Subject participation ends at this visit or if the subject is withdrawn from the study for any reason. The following procedures and assessments will be performed **during both phases of the study** at the end of the study and will be recorded on the subject eCRFs.

- Check and record AEs/SAEs and protocol deviations
- Collect the following from the medical and billing records (UB04):
  - Hospital History data
  - Healthcare Economic data
  - Resource Utilization data
- Verify data and enter into eCRF within 5 preferred business days of collection

**During the SM Phase only**, the following procedures and assessments will be performed.

- Remove BioModule, BioModule holder and electrodes. Discard disposable BioModule holder and electrodes.
- Clean reusable BioModule and return to the charging station
- Assess for and document any device deficiencies
- Subject complete Patient Satisfaction Questionnaire
- Eligible clinicians complete Clinical Team Satisfaction Questionnaire
- Eligible clinicians complete Telemetry Utilization Questionnaire for Clinicians (POST)
- Eligible clinicians complete Perception Questionnaire for Prescribing Clinicians (POST)

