### 6.2.2. Definition of Secondary Healthcare Economic and Resource Utilization Endpoints

1. Telemetry bed, ED, and ICU bed availability

**Definition:** Daily available number of beds available in both telemetry ED, and the ICU measured daily in hours from 12:00 AM to 11:59 PM.

2. Associated health care costs

**Definition:** Costs attributable to the primary and secondary clinical and resource utilization endpoints.

3. ICU, ED, PACU, and telemetry delays in transfer

**Definition:** Number of patients delayed admission to the ICU, ED, PACU, and to a telemetry bed.

4. Hospital unit transfers

**Definition:** Number of inpatient transfers from one unit to another unit during course of hospital stay.

5. Unplanned ICU transfers

**Definition:** Direct transfers from either study monitoring group to the ICU where the transfer was not planned during the hospital stay. For example, a transfer may be planned in advance of certain procedures for high risk patient as a preventative measure. The study team will determine if transfer were considered planned versus unplanned by review of the medical record.

6. LOS for ICU transfers

**Definition:** The LOS (time in minutes) in the ICU for subjects who have an unplanned transfer to the ICU.

7. Diagnostic tests and therapeutic procedures generated by artifacts and/or misdiagnosis

**Definition:** Any diagnostic test or therapeutic procedure that was performed because of an ECG artifact or misdiagnosis made by clinician using monitoring technology

This document is electronically controlled. Printed copies are considered uncontrolled.

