## 8.5. Product Training Requirements

Prior to investigation site activation or subsequent involvement in clinical study activities, Medtronic will provide product and clinical study training relevant and pertinent to the involvement of personnel conducting clinical study activities and investigator responsibilities.

As a minimum, Investigators and coordinators will be trained on their responsibilities, on the CIP, on the use of data collection tools as well as applicable local regulations. Study-specific training will be documented prior to investigation site activation. Hospital staff will be trained on the surveillance monitoring system prior to start of the SM phase of the study.

The support and training of the hospital units using the study product will be performed by employees of Medtronic.

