## 8.7. Product Return

The investigator will return used and unused study supplies and maintain documentation of return as instructed during the Site Initiation Visit training. Study supplies should be returned to: [REDACTED]

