## 8.8. Product Storage and Accountability

The investigator will store the study product per the instructions for use and product manual. The storage area should be locked/secure with access limited only to approved hospital and study staff. Devices should be stored in a way that they will not be mixed with standard clinical inventory.

Use of the study devices by each participant will be recorded on the PAL as instructed during the Site Initiation Visit training.

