## 10.11. Role of Sponsors Representatives

Sponsor's representatives may provide support as required for the clinical study, including technical support or training staff in the different hospital units. The sponsor will collaborate with investigator to implement the SM strategy which may include a sponsor implementation team to assist the site with adopting the SM strategy into their clinical workflow.

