## 15.2. Data Management

The investigator must ensure accuracy, completeness, and timeliness of the data reported in the CRFs and in all other required reports. Data reported on the eCRFs which are derived from source documents must be consistent with the source documents and discrepancies need to be justified in a documented rationale, signed and dated by the Principal Investigator, and filed in the subject medical file.

Only authorized persons can complete eCRFs. eCRFs shall be signed by the investigator (physicians only) as specified on the Delegated Tasks List included in the Investigator Site File.

The Electronic Data Capture (EDC) system maintains an audit trail on entries, changes or corrections in eCRFs. If a person is only authorized to complete eCRFs or make changes to an already signed eCRF, the investigator shall re-sign this eCRF.

The following data will be recorded directly on the eCRF and is considered as source data:

- Patient hospital billing data
- Hospital resource utilization data

Reports generated by Vital Sync™ IM & VPMP and raw data from the BioModule will be the source to determine the time of when a subject crossed protocol defined activation thresholds for clinical deterioration.

It is preferred that eCRFs will be completed within 5 business days from the performed visit or as soon as source documents are available, except for Serious Adverse Events that require immediate reporting and for Protocol Deviation requiring pre-approval. A delayed completion of the eCRF will not be considered a Protocol Deviation.

Data management will be done according to Medtronic SOPs that will be made available on request.

This document is electronically controlled. Printed copies are considered uncontrolled.

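### The cost comparison has no source for the cost of surveillance monitoring itself; if that cost is unbilled, leaving it out can only favour SM

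*Protocol*

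**What the plan says.** Protocol 6.1.2, objective 2, compares health care costs between the two monitoring periods. Protocol 6.2.2, item 2, repeated in SAP 4.2.2, defines them as "Costs attributable to the primary and secondary clinical and resource utilization endpoints".

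The sources are named in three places:
- Protocol 10.2: "Healthcare economic and resource utilization data will be collected separately via hospital and billing records".
- Protocol 10.2.3, for both phases: "Collect the following from the medical and billing records (UB04".
- Protocol 15.2: "Patient hospital billing data" and hospital resource utilization data are entered directly on the eCRF as source data.

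SAP 7.2 adds a health economic analysis built on data collected in the study, with the model inputs left open. SAP 7.11 (Health Outcomes Analyses) is marked not applicable.

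On how SM is supplied:
- Protocol 8.5: "The support and training of the hospital units using the study product will be performed by employees of Medtronic".
- Protocol 8.7: "The investigator will return used and unused study supplies and maintain documentation of return as instructed during the Site Initiation Visit training". The glossary entry for the Product Accountability Log (PAL) includes product sent back to the sponsor.
- Protocol 8.8: study devices are stored apart from the hospital's ordinary stock, and "Use of the study devices by each participant will be recorded on the PAL as instructed during the Site Initiation Visit training".
- Protocol 10.11: the sponsor helps put SM in place, "which may include a sponsor implementation team to assist the site with adopting the SM strategy into their clinical workflow".

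Telemetry in the control arm is the site's own standard care (Protocol 10.1).

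**The concern.** A cost comparison of two monitoring strategies should contain the cost of each strategy. Here one strategy is part of the hospital's routine operation. The other is delivered with study product that is logged, kept apart and returned, and with sponsor staff in support. Hospital records are a natural place to look for the cost of the first and an unlikely place to find the cost of the second.

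A hospital that adopted SM would have to obtain the sensors, holders, electrodes and software somehow. If those items are missing from the SM side, a statement that SM costs less would not describe what an adopting hospital would face. Health economics is part of the stated purpose (Protocol 5.2) and publication is planned (Protocol 15.9), so such a statement is likely to be read and used.

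**Working it through.** The plan states no cost figure for either arm, so there is nothing to reproduce. The check traces the cost inputs and then works out the direction of any omission.

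**1. What can enter the cost variable.** The sources are hospital, medical and billing records (Protocol 10.2, 10.2.3, 15.2). Neither document mentions a device price list, a sponsor cost record or a log of support hours.

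**2. What the definition brings in.** It covers costs attributable to the other endpoints: stay, bed availability, transfer delays, unit and ICU transfers, tests caused by artifact, RRT calls, codes, intubations. Monitoring equipment is not an endpoint, so the definition does not name its cost for either arm.

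**3. Whether SM product is likely to be on the bill.** Return, separate storage, per-participant accountability and sponsor-run training (Protocol 8.5 to 8.8, 10.11) fit study product supplied by the sponsor. No sentence says that the hospital is not charged.

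**4. Direction.** Let H be all other hospital cost per subject and M the monitoring cost, and let a and b be the shares of M found in the hospital records for SM and TM (each between 0 and 1).

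- True difference: (H_SM + M_SM) − (H_TM + M_TM)
- Recorded difference: (H_SM + a·M_SM) − (H_TM + b·M_TM)
- Recorded minus true: −(1 − a)·M_SM + (1 − b)·M_TM

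The first term is the SM omission. M_SM cannot be negative, so this term is zero or negative and moves the result only towards SM. The second term is zero if telemetry is fully captured. If telemetry is not captured either, the second term works the other way, and the net direction depends on figures the documents do not give.

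**5. Size.** With a = 0, the omitted recurring cost per SM subject is c × d, where c is the cost per device-day (pro-rated module and software, plus disposables) and d is device-days. The documents give neither. Illustration only, on assumed values c = 10 to 100 USD and d = 2 to 6:

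- lowest: 10 × 2 = 20 USD
- middle: 50 × 4 = 200 USD
- highest: 100 × 6 = 600 USD

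Two details bear on c and d. Modules are changed about every 24 hours because of the battery, then cleaned, recharged and reused; only holders and electrodes are discarded (Protocol Table 1, 10.2.2, 10.2.3). A module should therefore be pro-rated and not counted as a daily consumable. SM is also removed while a subject is on another unit (Protocol 10.1), so d is at most the enrolled stay.

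**6. One-off sponsor cost.** A fixed training and implementation cost F adds F/n per subject. At an assumed F = 100,000 USD this is 100,000/220 = 455 USD with the Protocol's maximum of 220 SM subjects and 100,000/140 = 714 USD with the SAP's 140. The figure depends mainly on how small the pilot is, which is a reason to keep it out of the main comparison.

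**The case against.** The best defence is that the definition treats both periods alike: it names monitoring technology for neither arm. Protocol 11.3 describes the devices as available in the hospitals, and Protocol 8.6 says none of the product is investigational. SAP 7.2 leaves the model inputs open, so PAL data could be used. Cost is one of 16 secondary objectives (7 + 9) in a single-centre pilot and has no hypothesis of its own.

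Part of this stands. A reader might infer that the bill itemises telemetry beds and telemetry charges while SM is free, so that the comparison favours SM by design. The documents do not support that: no section lists the content of the UB04 record, says that telemetry is billed separately, or says that SM is free to the site.

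A reader might also set the omission against the 204 USD in Protocol 5.1 and conclude that the sign could reverse. That figure is a cited opportunity cost in lost revenue when a patient waits more than three hours in the ED for a telemetry bed. It is not a saving this trial expects, and it says nothing about reversal.

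The rest does not remove the gap. The remark in Protocol 11.3 is part of a risk-benefit argument and not a statement about purchase. The SAP model is limited to data collected in the study; PAL counts could enter it, but no price is collected to value them. A definition that is silent for both arms still leaves the records to decide, by default, which arm's monitoring is counted.

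**Conclusion.** The plan has no input for the cost of SM devices, disposables or software. If those items are unbilled, which the supply rules imply but do not state, the cost comparison leaves them out, and that omission can only favour SM. A claim about the net bias would also need to know whether telemetry is fully captured in the hospital records, which the documents do not say.

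The size is unknown. The 20 to 600 USD per SM subject shown above is an illustration on assumed prices and device-days, and it cannot show that a saving would disappear or reverse.

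This is a specification gap in a secondary objective that is worth closing because closing it is cheap. The length-of-stay endpoint, its sample size and its test are not affected.

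**What to change.** In Protocol 6.2.2 item 2, SAP 4.2.2 and SAP 7.2:

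1. List the monitoring cost components for both arms (equipment, disposables, software, and the telemetry equivalents) and confirm with the hospital's finance records which of them are captured.
2. For each SM component that is not billed, add an imputed cost: device-days and disposables counted from the PAL, with reusable modules and software pro-rated, at a stated low-to-high price range. If a telemetry component turns out to be missing too, treat it the same way.
3. Report the cost difference with and without the imputed cost, and make no claim that SM costs less from the billing-only result alone.
4. Show one-off training and sponsor implementation cost only as a separate sensitivity analysis. The set-up cost of established telemetry is not counted, and spreading SM start-up over a small pilot would tilt the comparison the other way.

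The cost of the change is some wording, a short price table and a check that the PAL entries allow device-days to be derived. No new subject procedure is needed. The drawbacks are that the price will be an assumed or sponsor figure, hence the range, and that the SM cost result will look less favourable than billing alone would show.
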